# The HOPES Trial Version 5 02/23/2018

probability involves the potential GOSE scores for subjects with 4-week DRS observations, but have not reached their 6-month visit, and also potential GOSE scores for subjects with neither 4-week DRS nor 6-month GOSE scores (recent enrollees). The predictive probability accounts for the uncertainty in those two sets of incomplete subjects. If this probability is sufficiently high (indicating the current data, when complete, is very likely to produce a significant result) then the trial stops enrollment and follows the current subjects to completion.

The second predictive probability is the probability of trial success if the trial is continued to 350 subjects. In addition to the uncertainty for incomplete subjects, this predictive probability also incorporates uncertainty for subjects that have not yet enrolled, but will be enrolled in the future in order to reach a sample size of 350. If this probability is sufficient low (indicating that extending the trial to its maximum is unlikely to result in statistical significance) then the trial is discontinued for futility.

**9.5.2 Interim Analyses for Futility or Expected Success**. Interim analyses will occur at 31, 60,120,180, 240, and 300 subjects enrolled.

The analysis plan is as follows for the N=31 subjects:

When N=31 subjects are complete, we will observe the number of subjects on each arm (n\_ctrl and n\_trmt), and the number of observed successes on each arm Y\_ctrl and Y\_trmt. The predictive probability of success at N=60 subjects will be computed. This predictive probability incorporates uncertainty both in the true underlying treatment effect, for which we only have the random data on N=31 subjects, and the random variation in the N=29 potential future subjects in the trial. To compute this probability, we place noninformative Beta(0.5,0.5) priors on the true underlying success rates in both the control and treatment arms p\_ctrl and p\_trmt. The resulting posterior distributions based on the N=31 observations result in p\_ctrl | data ~ Beta(0.5+Y\_ctrl, 0.5+n\_ctrl-Y\_ctrl) and p\_trmt | data ~ Beta(0.5 + Y\_trmt, 0.5+n\_trmt-Y\_trmt) capturing the uncertainty in the true rates. Conditional on those rates, the future successes among the 29 remaining subjects will follow a Binomial distribution with a known number of future patients on each arm and the unknown true rate. Averaging across the uncertainty in the unknown true rate, we observe that the unknown number of future successes in each arm follows a Beta Binomial distribution.

These Beta Binomial predictive distributions provide the likely range of values for future observations. For example, if at the interim we observe 9 successes in 16 control patients, with 14 control patients remaining, we would observe that the true rate currently has a Beta(9.5,7.5) distribution and the number of future control successes is distributed BetaBinom(14,9.5,7.5), a distribution whose most likely value is 8/14 future successes, in line with our current observed rate and with approximately a 96-97% predictive probability the number of future successes will be between 3 and 12 inclusive, reflecting the high uncertainty in the true underlying rates and the sampling variability in the future subjects. The predictive distribution will likely have a high variance reflecting the small sample size at the interim. Performing this prediction for both the control and treatment arms, we may compute the predictive probability the future data will lie in a region where the final analysis will result in p<0.025 and trial success, known as the predictive probability of success.

This predictive probability will be provided to the DSMB. The trial should continue for predictive probabilities greater than 60% and stop for futility for predictive probabilities below 40%. If the

predictive probability is between 40-60% the DSMB will provide a recommendation for whether the trial should continue based on the totality of the evidence. The DSMB will only report "continue" or "stop for futility" to the sponsor to maintain blinding of the exact predictive probability.

The next interim analyses if applicable will be performed at 60,120,180, 240, and 300 subjects enrolled. At each interim analysis (60,120,180, 240, and 300 subjects enrolled), we will evaluate two predictive posterior probabilities:

Let ppnow be the predictive probability that the final efficacy analysis (Fisher's exact test) will be statistically significant if enrollment stops at the current sample size and all subjects are followed to the 6-month GOSE outcome. If this probability is sufficiently high, then enrollment will stop for expected success.

Let ppmax be the predictive probability that the final efficacy analysis (Fisher's exact test) will be statistically significant if enrollment continues to 350 patients and all subjects are followed to the 6-month GOSE outcome. If this probability is sufficiently low, then the trial will stop for futility.

Table 4 presents the stopping boundaries for the interim analyses. The trial will stop for success if ppnow exceeds the given success threshold, while the trial will stop for futility if ppmax is below the futility threshold. Note the values are calibrated to increase the likelihood of stopping at N=120 subjects. The trial has been powered to detect a moderately large effect at N=120 while maintaining the option of extending the trial should the results appear promising with a more moderate effect.

Table 4. Summary of Stopping Boundaries for Interim Analyses

	N=60	N=120	N=180	N=240	N=300
success	0.95	0.85	0.95	0.95	0.95
threshold for					
ppnow					
futility	0.10	0.40	0.10	0.10	0.10
threshold for					
ppmax					

The operating characteristics of this design (type I error, power, and expected sample size) were computed by simulation in a variety of possible scenarios. These scenarios were constructed by crossing four possible treatment effects with two possible relationships between 4-week DRS and 6-month GOSE scores (predictive and nonpredictive). Table 5 shows the values of the parameters for each of the simulated scenarios. In all scenarios the probability 6- month GOSE is good in the control arm is 0.347. In the *null* scenarios, scenarios where there is no difference between the scores, the probability 6-month GOSE is good in the treatment arm is also 0.347 (no treatment effect). We also consider low scenarios where the probability 6-month GOSE is good in the treatment arm is 0.498, medium scenarios where the probability 6-month GOSE is good in the treatment arm is 0.536, and alternative scenarios where the probability 6- month GOSE is good in the treatment arm is 0.604. The trial is powered for values closer to the 0.604 6-month scenario.

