#### 9.3 Sample Size and Accrual

A randomized design will be used in this study. Enrollment is intended to be N=120 but the trial allows an extension to a maximum of 350 patients randomized equally at a 1:1 ratio to each of two arms (hypothermia versus control). The final analysis will use a one-sided Fisher's exact test with significance level of 0.02 to compare proportions of patients with good outcome of GOSE at 6 months between two treatment arms. Interim analyses will be performed after 31, 60, 120, 180, 240, and 300 patients randomized. The 0.02 significance level has been calibrated to adjust for the multiple interim analyses and maintain an overall study type I error rate below 0.025. At each interim analysis, we will evaluate the predictive probability of statistical significance with the current sample size and with the maximum sample size. If the predictive probability of statistical significance with the current sample size is sufficiently high, then enrollment will stop and follow up will continue for 6 months. If the predictive probability of statistical significance with 350 patients is sufficiently low, then the study will stop for futility. Otherwise, enrollment will continue to the next analysis.

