# 9.4 Data Monitoring

A Data and Safety Monitoring Board (DSMB) will be established. The DSMB will include a biostatistician with expertise in research design and an expert in management of brain injured patients. Site PIs will monitor safety of each enrolled subject. In addition, safety analysis will be ongoing with interim monitoring for safety and study performance for every 20 patients or at least annually following the randomization of the first subject. Interim analysis for consideration of discontinuing the study for futility or discontinuing enrollment for predicted success will be performed after 31, 60, 120, 180, 240, and 300 patients have been randomized. Enrollment will be ongoing during this assessment.

Authorized representatives of the US Army Medical Research and Materiel Command (USAMRMC), who is one of the funding agency for this study, may review or obtain identifiable information (including the case ID number) related to participation in this research study for the purpose of monitoring the accuracy and completeness of the research data, for performing required scientific analyses of the research data, and as part of their responsibility to protect human research volunteers.

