We estimate these parameters in a Bayesian fashion, placing Beta(2,3) priors on pDc and pDt, Beta(1,4) priors on pGc0 and pGt0, and Beta(4,1) priors on pGc1 and pGt1. These priors reflect the historical data but are weak in that each prior has 5 observations worth of weight, meaning that accumulating data in contrast to the historical data above will result in inferences based on the current data, not the historical data. Thus this model is sufficiently flexible that it may be used when DRS is highly predictive of GOSE and also may be used if DRS is not predictive of GOSE.

The final analysis is a one-sided Fisher exact test with significance level 0.02 conducted only on the GOSE scores. Thus, the DRS values are only used in the analysis to predict GOSE scores for subjects who have a DRS score but not a GOSE score. For the final analysis, 6-month GOSE scores will be used. If the 6-month GOSE score is missing the 4-week DRS score will be used to impute the 6-month GOSE score.

At each interim analysis we compute two predictive probabilities. The first is the predictive probability of trial success if enrollment stops, the current subjects are followed to completion, and the Fisher's exact test is conducted on the final data. For this predictive probability many of the subjects will have 6-month GOSE scores reported. The uncertainty in the predictive

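### The N=31 futility calculation counts success at p<0.025 although the final test is at 0.02, and its trigger is 31 complete in one place but 31 randomised or enrolled in others

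*Combined protocol and SAP*

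**What the plan says.** **Level.** Section 9.5.1: "The final analysis is a one-sided Fisher exact test with significance level 0.02 conducted only on the GOSE scores". The Synopsis and Section 9.3 give the same level, and Section 9.3 gives the reason: "The 0.02 significance level has been calibrated to adjust for the multiple interim analyses", keeping the overall error below 0.025. The N=31 plan in Section 9.5.2 instead sums the predictive distribution over results for which "the final analysis will result in p<0.025 and trial success". It gives no reason for the different level and does not restate the sidedness.

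**Trigger.** The N=31 plan opens "When N=31 subjects are complete" and treats as random, besides the true effect, "the random variation in the N=29 potential future subjects in the trial". Section 9.3 says "Interim analyses will be performed after 31, 60, 120, 180, 240, and 300 patients randomized". Section 9.4 says the looks are "performed after 31, 60, 120, 180, 240, and 300 patients have been randomized" and adds "Enrollment will be ongoing during this assessment". The first sentence of Section 9.5.2 counts subjects enrolled.

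**Method and rule.** The N=31 calculation uses GOSE alone, with a Beta(0.5,0.5) prior in each arm and N=60 as the horizon. Above 60% the trial continues, below 40% it stops for futility, and in between the DSMB advises. Sections 3, 9.5 and 9.5.1 describe interim analyses that use the 4-week DRS for subjects whose GOSE is pending.

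**The concern.** The look at 31 can end the trial, so the figure given to the DSMB should refer to the test the trial will run. Here 0.025, the overall error budget, stands where the nominal level of 0.02 belongs.

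The trigger matters for a different reason. The formula needs the number of GOSE successes among 31 subjects whose outcome is known. At 31 randomised, recent enrollees have no 6-month score, so the formula cannot be applied as written. At 31 complete with enrolment open, other subjects are already in the trial, some with a 4-week DRS. The N=31 text does not say what is done with them, although other sections say that interim analyses use such data.

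**Working it through.** **1. The plan's own example.** Control 9/16 with 14 to come gives BetaBinom(14, 9.5, 7.5). The mode is 8 and P(3 to 12) = 0.966. Both agree with the plan (8 of 14; about 96-97%).

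**2. Effect of the level.** Inputs are 16 control and 15 treated complete (16 control as in the plan's example), 30 per arm at N=60 (1:1 allocation), and Beta(0.5,0.5) priors. With Yc and Yt successes so far,

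PP(α) = Σa Σb BB(a; 14, 0.5+Yc, 16.5−Yc) × BB(b; 15, 0.5+Yt, 15.5−Yt) × 1[one-sided Fisher p(Yc+a, Yt+b; 30, 30) < α].

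Fisher's test is discrete, so at 30 per arm the two levels have different critical values for only four control counts: 2, 5, 17 and 21 of 30.

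Over all 17 × 16 = 272 possible results:

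- The largest shift is 4.9 points (control 11/16, treated 14/15: 0.491 at 0.02, 0.540 at 0.025). Both values lie in the discretion band.
- One result changes band: control 1/16, treated 5/15, from 0.641 at 0.025 (continue) to 0.595 at 0.02 (DSMB discretion).
- Its probability with 0.347 in both arms is [16 × 0.347 × 0.653^15] × [3003 × 0.347^5 × 0.653^10] = 0.0093 × 0.213 = 0.0020. With treatment rates of 0.498, 0.536 and 0.604 it is 0.0009, 0.0006 and 0.0002.
- P(PP below 40%) is the same under either level:

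| Treatment rate (control 0.347) | P(stop) at 0.02 | P(stop) at 0.025 |
|---|---|---|
| 0.347 | 0.927 | 0.927 |
| 0.498 | 0.717 | 0.717 |
| 0.536 | 0.641 | 0.641 |
| 0.604 | 0.492 | 0.492 |

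For splits from 12/19 to 19/12, one or two results change band and the largest shift is 5.2 points. At 15/16 the one change is again between continue and discretion. At splits of 14/17 or more uneven, in either direction, one result does cross the 40% line. For example, with 14 control and 17 treated, control 1 and treated 5 gives 0.389 at 0.02 and 0.438 at 0.025.

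**3. Trigger.** The documents give no accrual rate. Assume r patients per month and a 6-month outcome, and ignore the 3-week window and early deaths.

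| r per month | Without 6-month GOSE at 31 randomised (6r) | Enrolled when the 31st completes (31 + 6r) |
|---|---|---|
| 1 | 6 | 37 |
| 2 | 12 | 43 |
| 3 | 18 | 49 |
| 4 | 24 | 55 |
| 5 | 30 | 61 |

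Most of the 31 lack a GOSE once 6r > 15.5, that is, above about 2.6 per month. More than 60 are enrolled at the 31st completion only if r > 29/6 = 4.8 per month.

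**4. Pending DRS.** The 9.5.1 model and its priors were held fixed, and the decision was compared with and without the DRS of enrolled subjects. Assumptions: level 0.02, Table 5 predictive scenarios, 16/15 split, 30 per arm at N=60, DRS available after one month, 2 to 5 patients per month, 2,000 simulated trials per case. With 0.347 versus 0.604 the band changes in about 22% to 27% of trials. In about 8% to 11% a stop becomes something else, and in about 5% to 7% the reverse happens. Under the null the band changes in 5% or fewer.

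**The case against.** Several stronger readings are tempting, and the documents do not support them.

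- *The 0.025 level distorts the stopping decision.* It does not at the near-even splits checked, 16/15 and 15/16, where no result crosses the 40% line. Nor can it raise the type I error: this look can only continue or stop for futility, and the final test stays at 0.02.
- *The level matters more at a larger final sample.* The N=31 text fixes the horizon at N=60, so power comparisons at other sample sizes say nothing about this figure.
- *The 29 is wrong because some of those subjects are already enrolled.* With 31 outcomes known out of 60, 29 are unknown whether or not the subjects have been enrolled, and the beta-binomial step is valid for both. The count fails only if more than 60 are enrolled by then, which needs about 5 per month.
- *The look must use the DRS model.* Section 9.5.2 sets out a separate GOSE-only calculation with noninformative priors and then describes the later looks on their own. That may be deliberate. Leaving out pending DRS loses information but does not make the calculation invalid.

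It can also be said that the specific N=31 text governs the trigger and that the other sections merely list sample sizes. That is a reasonable reading, but nothing in the plan says so. The DRS point stands only as a conflict to settle: Section 9.5.1 describes its method for each interim analysis, and the N=31 text departs from it without comment.

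**Conclusion.** Both inconsistencies are in the current text and should be corrected. The success level is a specification error of little consequence: at most 4.9 points, one of 272 results changing band with probability 0.2% or less, and no stop decision changed. These figures rest on a 16/15 split and 30 per arm at N=60; at more uneven splits an isolated result can cross the 40% line.

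The trigger is the more practical problem, because under the 31-randomised or 31-enrolled wording the stated formula lacks some of its inputs. How many depends on accrual, which the documents do not give.

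How pending DRS is handled could change roughly a quarter of N=31 decisions if the treatment works as powered for. That figure depends on assumed accrual and on DRS predicting GOSE as in the historical data. It shows that the choice should be written down; it does not show which choice is right.

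**What to change.** 1. In the N=31 text of Section 9.5.2, replace p<0.025 with the one-sided 0.02 level of the final test. This is a one-number correction.
2. State one trigger in Sections 9.3, 9.4 and 9.5.2: 31 subjects with known 6-month GOSE. This is one phrase in each place.
3. Add a sentence on subjects enrolled but not complete at that time, reconciling the N=31 text with Sections 3, 9.5 and 9.5.1. There are two options for the sponsor to choose between:
   - Keep the GOSE-only beta-binomial and say that this is intended. It costs nothing to implement but discards DRS data in hand.
   - Use the 9.5.1 model. The code for the later looks can be adapted, but this replaces Beta(0.5,0.5) with the weak historical priors Beta(2,3), Beta(1,4) and Beta(4,1). It changes a stopping rule, so it is more than a wording edit, and the behaviour of the look should be recomputed.
4. Say what happens if more than 60 subjects are enrolled when the 31st completes, since the count of 29 and the N=60 horizon would then no longer apply.

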# HypOthermia for Patients requiring Evacuation of Subdural Hematoma: a Multicenter, Randomized Clinical Trial

#### "The HOPES Trial"

#### 1. STUDY OBJECTIVES

# 1.1 Primary Objective

The primary objective is to determine if rapid induction of hypothermia prior to emergent craniotomy for traumatic subdural hematomas (SDH) will improve outcomes as measured by Glasgow Outcome Scale-Extended (GOSE) at 6 months. Treatment with hypothermia will lead to at least a 15% improvement in good outcomes. The primary outcome measure will be a dichotomized GOSE at 6 months.

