# The HOPES Trial Version 5 02/23/2018

In the non-predictive scenarios, 6-month GOSE and 4-week DRS scores are independent, while in the predictive scenarios the relationship between 6-month GOSE and 4-week DRS is equal to the observed relationship in the historical data above.

Table 5. The values of the parameters in each of the eight simulated scenarios

	pDc	pDt	pGc0	pGc1	pGt0	pGt1	Pr(GOSE	Pr(GOSE
							good in	good in
							ctrl)	trmt)
Null Pred.	0.40	0.40	0.045	0.800	0.045	0.800	0.347	0.347
Null Non.	0.50	0.50	0.347	0.347	0.347	0.347	0.347	0.347
Low Pred.	0.40	0.60	0.045	0.800	0.045	0.800	0.347	0.498
Low Non.	0.50	0.50	0.347	0.347	0.498	0.498	0.347	0.498
Med Pred.	0.40	0.65	0.045	0.800	0.045	0.800	0.347	0.536
Med Non.	0.50	0.50	0.347	0.347	0.536	0.536	0.347	0.536
Alt Pred.	0.40	0.74	0.045	0.800	0.045	0.800	0.347	0.604
Alt None.	0.50	0.50	0.347	0.347	0.604	0.604	0.347	0.604

The table below provides the operating characteristics (probabilities of success or futility at each possible sample size). As noted above, the trial is powered for effect sizes closer to the "alternative" scenarios, where the trial has over 90% power and a high likelihood of stopping (typically for success) at or before the N=120 interim analysis. Similarly, type I error is controlled at 0.025 for the null scenarios and they are quite likely to stop (typically for futility) at or before the N=120 interim analysis. Power is as expected reduced for effect sizes below where the trial is powered, although the medium scenarios still retain power in the 75-80% range.

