Operating characteristics for each of the eight scenarios is summarized in Table 6. The first column provides the scenario name, while the next 6 columns (N=60 through N=350) provides the probability of futility (top number in each cell) and success (bottom number in each cell) at those sample sizes. Thus, for example, in the low predictive scenario the probability of stopping at N=120 and having a successful trial is 0.179. The expected sample size for each trial is given in the E[N] column while the probability of trial success (the sum of the bottom numbers in the N=60 through N=350 cells) is given in the Pr(success) column. The trial is powered for the alternative (bottom two) scenarios, where power is over 90%, although the trial retains modest (75-80%) power for more moderate effect sizes. In the null and alternative scenarios the trial is quite likely to stop at or before the N=120 interim analysis. Results in this table were computed by simulating 10,000 trials in each scenario.

Table 6. Operating Characteristics

	 		1					1
	N=60	N=120	N=180	N=240	N=300	N=350	E[N]	Pr(success)
Null Pred	0.344	0.513	0.024	0.039	0.030	0.026	118.3	0.024
	0.003	0.009	0.004	0.002	0.002	0.004		
Null Non	0.322	0.527	0.026	0.042	0.033	0.030	121.9	0.021
	0.002	0.006	0.003	0.003	0.001	0.005		
Low Pred	0.061	0.227	0.006	0.012	0.016	0.040	180.0	0.637
	0.057	0.179	0.136	0.114	0.075	0.078		
Low Non	0.083	0.248	0.007	0.013	0.013	0.042	182.8	0.594
	0.030	0.160	0.125	0.112	0.077	0.091		
Med Pred	0.035	0.137	0.003	0.005	0.006	0.016	166.9	0.798
	0.088	0.289	0.179	0.130	0.068	0.044		
Med Non	0.053	0.165	0.004	0.005	0.005	0.014	173.3	0.756
	0.050	0.254	0.178	0.138	0.078	0.059		
Alt Pred	0.014	0.042	0.001	0.000	0.000	0.001	134.3	0.942
	0.200	0.438	0.195	0.083	0.019	0.007		
Alt Non	0.024	0.058	0.000	0.000	0.000	0.001	143.2	0.917
	0.115	0.452	0.220	0.096	0.025	0.009		

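### The N=31 futility rule is missing from the simulated operating characteristics; if followed, it cuts power at the design alternative from over 90% to about 50%

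*Combined protocol and SAP*

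**What the plan says.** Sections 9.3, 9.4 and 9.5.2 list interim analyses at 31, 60, 120, 180, 240 and 300 patients; the synopsis lists them from 60 only.

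Section 9.5.2 gives N=31 its own rule. With Beta(0.5, 0.5) priors in each arm, "The predictive probability of success at N=60 subjects will be computed", where success means that "the final analysis will result in p<0.025 and trial success". Then: "The trial should continue for predictive probabilities greater than 60% and stop for futility for predictive probabilities below 40" (per cent). Between 40 and 60% the DSMB makes a recommendation.

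The later looks work differently. Futility depends on ppmax, the predictive probability of success at 350 patients; the threshold is 0.10, except 0.40 at N=120 (Table 4). Section 9.5.1 sets the final test: "The final analysis is a one-sided Fisher exact test with significance level 0.02 conducted only on the GOSE scores".

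On power, the text before Table 6 describes the alternative scenarios as those "where the trial has over 90% power and a high likelihood of stopping" by N=120, and the text on Table 6 repeats: "The trial is powered for the alternative (bottom two) scenarios, where power is over 90" (per cent). Table 6 gives 0.942 (DRS predictive) and 0.917 (non-predictive). Its columns run from N=60 to N=350.

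**The concern.** A scheduled look that can end the trial is absent from the simulations behind the power claim. It also sets a hurdle that the design is not built to clear. Section 9.5.2 says the trial is powered for a moderately large effect at N=120, with extension if results are promising. The N=31 rule instead asks whether the trial is likely to win at N=60, where power is low even for the full alternative.

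At stake is a trial described as having over 90% power that has about even odds of a futility recommendation on 31 patients' data when hypothermia works exactly as hypothesised. The DSMB would apply the rule without any simulated figure showing what it costs.

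**Working it through.** **Inputs (all from Section 9).** Control rate: "In all scenarios the probability 6- month GOSE is good in the control arm is 0.347". Treatment rates are 0.347 (null), 0.498 (low), 0.536 (medium) and 0.604 (alternative). Allocation is 1:1. The worked example in 9.5.2 has 16 control patients with 14 to come, so I use 16 control/15 treated, and also 15/16, with a target of 30 per arm. Accrual is not stated and is needed only in step 5.

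**1. Does Table 6 leave room for a stop at 31?** Adding futility and success probabilities from N=60 to N=350:

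- Alt Pred: 0.058 + 0.942 = 1.000
- Alt Non: 0.083 + 0.917 = 1.000
- Null Pred: 0.976 + 0.024 = 1.000

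No probability remains for a stop at N=31.

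**2. The plan's own example.** BetaBinomial(14, 9.5, 7.5) has its mode at 8 and P(3 to 12) = 0.966, matching the stated 8/14 and 96-97%.

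**3. Exact stopping probability at N=31.** For each pair (y_c, y_t), future successes follow BetaBinomial(30 − n, 0.5 + y, 0.5 + n − y) independently in each arm. PP60 is the probability that one-sided Fisher at 30 v 30 gives p<0.025. Weighting the pairs by their binomial probabilities gives (16/15 split, then 15/16):

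| Scenario | P(PP60<40%) | P(PP60>60%) | Most power possible, 1 − P(PP60<40%) | Table 6 power (Pred, Non) |
|---|---|---|---|---|
| Null | 0.93, 0.93 | 0.03, 0.04 | – | – |
| Low | 0.72, 0.73 | 0.17, 0.17 | 0.28, 0.27 | 0.637, 0.594 |
| Medium | 0.64, 0.65 | 0.23, 0.23 | 0.36, 0.35 | 0.798, 0.756 |
| Alternative | 0.492, 0.498 | 0.363, 0.359 | 0.51, 0.50 | 0.942, 0.917 |

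The fourth column needs no accrual assumption: a trial stopped for futility cannot succeed. If the DSMB also stops throughout the 40-60% zone, the limit is the third column, 0.36 at the alternative. The low scenario (0.498 − 0.347 = 0.151) is about the effect in Section 1.1: "Treatment with hypothermia will lead to at least a 15% improvement in good outcomes".

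Replacing 0.025 by the final test's 0.02 leaves P(PP60<40%) unchanged to three decimals.

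**4. Why the rule is so severe.** Exact one-sided Fisher power at 30 per arm for 0.347 v 0.604 is 0.42. Two interim results show the effect:

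- 5/16 v 8/15 (31% v 53%): PP60 = 0.29, stop; predictive probability of success at 350 = 0.73.
- 6/16 v 9/15 (37.5% v 60%, close to the planned effect): PP60 = 0.30, stop; at 350, 0.73.

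Among alternative-scenario trials stopped at N=31, 96% (16/15 split) have a predictive probability at 350 of at least 0.10; the mean is 0.51. These use the same Beta(0.5, 0.5) priors and Fisher at 0.02.

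**5. Full design by simulation.** I used the 9.5.1 model and Table 4 thresholds, with DRS at 1 month, GOSE at 6 months and 10,000 trials. Accrual of 2 patients/month is an assumption.

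- Without the N=31 look: Alt Pred 0.945 (stated 0.942) and Alt Non 0.927 (stated 0.917). At 2.5/month they are 0.944 and 0.917. The medium scenarios give 0.79 and 0.76 (stated 0.798, 0.756).
- With the look, DSMB continuing at 40-60%: alternative 0.49-0.50, medium about 0.33, low 0.23-0.24.
- With the look, DSMB stopping at 40-60%: alternative 0.35-0.36.
- Null: type I error falls from about 0.02 to 0.007-0.009.

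At 2, 5 and 8 patients/month, or with all outcomes complete, alternative power under the rule stays at 0.49-0.52, although the baseline without it ranges from 0.85 to 0.96.

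**The case against.** Five points can be made for the plan.

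- **The N=31 rule is separate by design.** Section 9.5.2 sets it apart from the looks at 60 to 300, so a different criterion there is not in itself a contradiction. A sponsor may want a demanding early hurdle to limit exposure or cost. This stands, and it makes a change of rule optional. It does not rescue the power statement: the documents give no such rationale, and a deliberate hurdle still has to be in the simulations.
- **The rule is advisory.** It says the trial should stop, and 40-60% is left to judgement. This stands: the loss applies to the extent that the DSMB follows the rule, and power is higher if it overrides. It is still the pre-specified instruction.
- **Futility stopping does not inflate type I error.** Correct. The misstated quantities are power, expected sample size and stopping probabilities.
- **Timing.** Sections 9.3 and 9.4 count 31 randomised, but the rule operates when 31 are complete. At 2/month about 31 + 12 = 43 would be enrolled by then. Above (60 − 31)/6 ≈ 4.8/month, 60 would be randomised first. The figures here apply the N=31 rule first. The plan should settle the order.
- **The 0.025/0.02 mismatch is immaterial.** Agreed; it is a wording correction.

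**Conclusion.** The concern holds. Table 6 excludes a scheduled look, so its over-90% power does not describe the plan as written. At 0.347 v 0.604, power under the rule is about 0.50 (at most 0.51) if the DSMB continues every trial in the 40-60% zone, and about 0.36 if it stops them all: a shortfall of more than 40 percentage points either way. The medium and low scenarios lose a similar share or more.

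The limit rests on the plan's own priors, target and thresholds, a near-equal split at 31, adherence to the rule, and the N=31 look preceding the N=60 look. It does not depend on accrual; the simulated figures assume a rate but barely move across 2 to 8 patients/month.

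**What to change.** **Necessary.** Add the N=31 look to Table 4 and re-run Table 6 with it. Restate power, type I error and expected sample size, showing the 40-60% zone both as always continue and as always stop. Remove the over-90% claim if the rule stays. Align the list of looks in the synopsis with Section 9, state whether 31 means randomised or complete, and use 0.02 in the N=31 calculation. The cost is a simulation re-run and wording, with a much less favourable power figure if the rule is kept.

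**Recommended, but a design choice.** Base the N=31 decision on ppmax, stopping only below 0.10 (success at 350, Fisher 0.02). By exact enumeration this stops about 2% of alternative trials and 25-31% of null trials, depending on the split. Simulated power is then 0.93 (predictive) and 0.91 (non-predictive). The price is that far fewer null trials stop at this look (25-31% instead of 93%). The effect on expected sample size should come from the sponsor's own re-run, counting patients enrolled while the first 31 mature. No extra patients are needed at the planned maximum.
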